2.7 Statistical Analysis

Continuous variables will be reported as mean \pm standard deviation and where appropriate as median \pm interquartile range. Continuous variables were compared with unpaired t-test, and proportions were compared with the chi-square test. A two-sided p-value of $< .05$ was considered to indicate a statistically significant difference. For the secondary effectiveness endpoint of freedom from AF from the 90-day post-procedure blanking period through 12 months of follow-up, the length of time to recurrence of AF in each group was analyzed using Kaplan-Meier curves. Data were managed using Microsoft Excel and statistical analyses calculated using Microsoft Excel or Matlab.

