1 PROTOCOL SUMMARY

Objective	The objective of this study is to evaluate the reliability of the Ablacon Electrographic Flow (EGF) algorithm technology (Ablamap® Software) to identify AF sources and guide ablation therapy in patients with persistent atrial fibrillation
Test Device	Ablacon Electrographic Flow Algorithm Technology (Ablamap® Software)
Study Design	The study is a prospective, randomized, controlled multi-center study.
Planned Subject Sample Size	A maximum of 100 subjects will be enrolled in this study.
No. of Sites	Subjects will be enrolled at up to five (5) investigational sites in Europe.
Primary Safety Endpoint	Freedom from serious adverse events (SAEs) related to the procedure through 7 days following the Randomization procedure.
Primary Efficacy Endpoint	Acute procedure success defined as the ability to successfully ablate AF sources identified by the Ablacon EGF algorithm
Secondary Efficacy Endpoints	
 • Consistency of sources identified by the Ablacon EGF algorithm between the randomization procedure and any applicable subsequent EGF-guided ablation procedures as assessed by remapping of the atria and the algorithm's ability to reproduce sources identified by a previous procedure • Freedom from documented episodes of atrial fibrillation recurrence following the blanking period (90 days post procedure through 12 months). • Total number of EGF source ablations • Total time of EGF source ablations • Total fluoroscopy time and dose • Overall procedure time
Inclusion Criteria	
 1. Suitable candidate for intra-cardiac mapping and ablation of atrial arrhythmias. 2. Above eighteen (18) years of age or of legal age to give informed consent specific to state and national law. 3. Subjects with a history of documented symptomatic, persistent or longstanding persistent atrial fibrillation ≤ 36 months. 4. Subject agrees to comply with study procedures and be available (geographically stable) for follow-up visits for at least 12 months.

	
5. Treatment of atrial fibrillation with ablation therapy presenting with recurrent symptoms of AF (not applicable to De Novo subjects)
																

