2.2 Primary Endpoints

The primary endpoint events for this trial to assess the safety and effectiveness of the Ablamap® Software System to guide therapy for the treatment of persistent atrial fibrillation are as follows:

- Primary Safety Endpoint: Freedom from serious adverse events (SAEs) related to the procedure through 7 days following the Randomization procedure.
- Primary Effectiveness Endpoint: Acute procedure success defined as the ability to successfully ablate AF sources identified by the EGF algorithm.

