2.5 Enrollment/Screen Failures

A subject is considered enrolled after signing the informed consent. All enrolled subjects will then proceed to complete the screening and baseline tests. If they do not meet the eligibility criteria, they will be exited from the study and will not count towards the treated study population.

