2.6 Randomization

A 1:1 blocked randomization scheme stratified by site will be used for randomization. Subjects will be randomized based on the results of the pre-procedure EGF mapping procedure. If the subject has identifiable AF sources above a pre-specified threshold, the subject will be randomized to either: 1) immediate EGF-guided radiofrequency ablation with the Ablamap® Software System; or 2) EGF mapping followed by a cardioversion procedure, if required. If the subject is randomized to no treatment, the investigator may choose to cardiovert the subject prior to ending the procedure. Subjects that have no identifiable sources or sources below the threshold will not be randomized. The investigator may choose to ablate those subjects per their standard ablation practices.

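### Primary safety has no interval estimate: the only applicable analysis is a generic chi-square test, and with at most 50 per arm a non-significant result could not support a safety conclusion

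*Combined protocol and SAP*

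**What the plan says.** Section 2.2 defines the primary safety endpoint as "Freedom from serious adverse events (SAEs) related to the procedure through 7 days following the Randomization procedure". This is a yes/no outcome per subject, so the result is a proportion. The section attaches no comparator, margin, acceptable rate or analysis set.

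Section 2.7 is the whole analysis plan. For proportions it says only that "proportions were compared with the chi-square test", with the criterion "A two-sided p-value of $< .05$ was considered to indicate a statistically significant difference". It does not mention the safety endpoint and asks for no confidence interval on any proportion.

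Three further statements limit the numbers:

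- Protocol summary: "A maximum of 100 subjects will be enrolled in this study".
- Section 2.5: "A subject is considered enrolled after signing the informed consent". Subjects who fail screening may therefore use up part of the 100.
- Section 2.6: "A 1:1 blocked randomization scheme stratified by site will be used for randomization", but "Subjects that have no identifiable sources or sources below the threshold will not be randomized".

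**The concern.** A significance test asks whether the data are incompatible with equal SAE rates. A safety endpoint needs a different answer: how high the rate, or the excess over control, could still be. With small arms and uncommon events the two come apart, because a test can be non-significant while a large excess remains possible.

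The introduction says that EGF-guided ablation of AF sources has not yet been performed in a controlled trial. Under section 2.6 one randomized arm is ablated at once, and the other is mapped and cardioverted if required. A true difference in procedure-related SAEs is therefore plausible, and its possible size is what readers of this trial will want to know. As written, the plan need not report it.

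**Working it through.** **Plan's own figure.** The only sample-size figure is 100. It comes with no event rate, effect size, margin or power, so there is nothing to reproduce it from.

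**Inputs**

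- Subjects per arm: at most 100 / 2 = 50 (protocol summary; 1:1 allocation in section 2.6). The number lost to screening and to the source threshold is not stated, so I assume 25 to 50 per arm.
- Test: Pearson chi-square without continuity correction, two-sided .05 (section 2.7; the absence of a correction is my assumption).
- SAE rates: not in the documents. I assume 10% vs 2%, 5% vs 1% and 10% vs 0% (ablation vs control).

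**Step 1: power to show an excess.** For a and b events in arms of n, with pooled p = (a + b)/(2n), the statistic is

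X² = (a/n − b/n)² / [p(1 − p)(2/n)].

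Power is the sum, over all tables with X² above the 5% critical value and a > b, of Bin(a; n, p₁) × Bin(b; n, p₀).

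| Assumed rates | n = 25 | n = 30 | n = 40 | n = 50 |
|---|---|---|---|---|
| 10% vs 2% | 15% | 22% | 34% | 38% |
| 5% vs 1% | 3% | 5% | 10% | 15% |
| 10% vs 0% | 24% | 35% | 58% | 75% |

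The last row can be checked by hand. With no control events, 4 events in the ablation arm are the fewest that give p < .05 at each of these sizes. Power at n = 50 is therefore P(Bin(50, 0.10) ≥ 4) = 1 − 0.25 = 75%.

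**Step 2: what a non-significant result leaves open.** Take 3/40 vs 0/40, so p = 3/80 = 0.0375.

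- X² = 0.075² / (0.0375 × 0.9625 × 0.05) = 0.005625 / 0.001805 = 3.12, which gives p = .077.
- The Wilson 95% limits are 2.6% to 19.9% for 3/40 and 0% to 8.8% for 0/40.
- Newcombe lower limit: 7.5 − √[(7.5 − 2.6)² + (8.8 − 0)²] = −2.5 points (unrounded inputs).
- Newcombe upper limit: 7.5 + √[(19.9 − 7.5)² + 0²] = +19.9 points.

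The test is non-significant, yet an excess of about 20 points is not excluded.

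**Step 3: the most favourable result.** With 0 events in n subjects, the two-sided exact (Clopper-Pearson) 95% upper limit is 1 − 0.025^(1/n):

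| n | 25 | 30 | 40 | 50 |
|---|---|---|---|---|
| Upper limit | 13.7% | 11.6% | 8.8% | 7.1% |

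An arm with no SAEs at all still leaves a true rate of 7% to 14% possible, and the documents give no acceptable rate to compare this with.

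**The case against.** **The plan never says that non-significance means safe.** A reader might infer that p ≥ .05 is meant to be the safety result. The documents do not support that. Section 2.7 says only what p < .05 indicates, and does not tie the chi-square test to the safety endpoint. This objection stands: how the result would be interpreted cannot be predicted from the text. It does not remove the gap. If the chi-square sentence was not meant for safety, the primary safety endpoint has no stated analysis at all.

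**The chi-square test is not shown to be invalid.** A reader might also infer this from the sparse cells. With equal arms, fewer than 10 SAEs in total puts both expected SAE counts below 5. That rule of thumb does not show a material error here:

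- For 4/40 vs 0/40, chi-square gives p = .040 and Barnard's unconditional exact test gives .043.
- When both true rates are 2%, the actual two-sided size is 0.2% at 25 per arm and 1.3% at 50, so the test is conservative.
- At 40 per arm, with common rates from 1% to 19%, the size does not exceed 5.9%.

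Nor would a more conservative exact test help. Boschloo's test gives .082 for the same 4/40 vs 0/40 table, so it would make an excess harder to show.

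**The power figures rest on assumed rates.** This stands. The control arm has no ablation at the randomization procedure, so a control rate near zero is plausible, and power then reaches 75% for 10% vs 0% at 50 per arm. Very large excesses would usually be found: for 20% vs 2% at 50 per arm, power is 89%. The claim is limited to moderate excesses and small arms.

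**Low power comes from the sample size, and a different analysis adds no information.** This is true. An interval does not make the trial more informative, but it does show what the trial can and cannot exclude.

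**Conclusion.** The concern holds as a gap in estimation. Section 2.7 offers only a generic two-sided test for the primary safety proportion and no interval. With 25 to 50 per arm, a non-significant result could not support a conclusion of safety. The power range across the three assumed pairs of rates is 3% to 75%. The interval results in steps 2 and 3 need no assumed SAE rate, only an arm size and an event count, and they carry the point: an excess of about 20 points remains possible at 3/40 vs 0/40, and a rate of 7.1% to 13.7% remains possible with no events.

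The arm-size range is itself an assumption below the ceiling of 50. The point does not depend on the chi-square approximation being wrong, or on anyone intending to read p ≥ .05 as proof of safety. It is an inexpensive improvement that should be made.

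**What to change.** In section 2.7, add a paragraph for the primary safety endpoint that:

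- makes estimation the primary safety analysis, reporting the procedure-related SAE rate through 7 days in each randomized arm with its exact (Clopper-Pearson) 95% confidence interval;
- gives the difference between arms with a Newcombe or score 95% confidence interval;
- labels any p-value for this endpoint as descriptive, and states that p ≥ .05 will not be read as evidence of safety.

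The cost is a few lines of SAP text and trivial computing. No extra subjects or data are needed. The drawback is that the intervals will be visibly wide, which is an accurate picture of what a trial of this size can say about safety.

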3 SUBJECT SELECTION

3.1 Patient Selection-Criteria for Eligibility

Subjects enrolled in the FLOW-AF Study should be selected from the investigators' general patient population with a history of persistent atrial fibrillation that meet eligibility criteria. Patient selection may also be performed by review of the medical records of those subjects whom have had prior AF treatment with ablation therapy. Investigators are responsible for screening all potential subjects and selecting those who meet the eligibility criteria for the study.

3.1.1 Study Inclusion Criteria

Subjects must have met ALL of the following criteria:

1. Suitable candidate for intra-cardiac mapping and ablation of arrhythmias.
2. Above eighteen (18) years of age or of legal age to give informed consent specific to state and national law.
3. Subjects with a history of documented symptomatic, persistent or longstanding AF ≤ 36 months.
4. Subject agrees to comply with study procedures and be available (geographically stable) for follow-up visits for at least 12 months
5. Treatment of AF with ablation therapy presenting with recurrent symptoms of AF (not applicable to De Novo subjects).

3.1.2 Study Exclusion Criteria

Candidates were excluded from the study if any of the following applied:

- LA diameter > 5.5 cm.
- Left ventricular ejection fraction (LVEF) $< 35\%$
- Presence of intramural thrombus, tumor or abnormality that precludes vascular access, catheter introduction or manipulation
- Coagulopathy, bleeding diathesis or suspected procoagulant state
- Known allergies or intolerance to anticoagulant and antiplatelet therapies to be used in conjunction with the study or contrast sensitivity that cannot be adequately pre-treated prior to the ablation procedure

- Positive pregnancy test results for female patients of childbearing potential or breast feeding
- Acute or chronic medical condition that in the judgment of the investigator would increase risk to the patient or deem the patient inappropriate to participate in the study
- Mitral valve stenosis and/or severe mitral regurgitation
- Valvular AF
- Prosthetic valves
- NYHA Class IV
- History of MI within 3 months prior to procedure
- ASD or LAA closure device.
- AF from a reversible cause (e.g., surgery, hyperthyroidism, sarcoidosis or pericarditis)
- Life expectancy < 12 months based on medical history or the medical judgement of the investigator
- Presence of any transvenous pacing ICD or CRT leads.

3.2 Study Assessments

The tests and measurements that were conducted at baseline, during the treatment procedure, and during follow-up visits are illustrated in **Table 1**.

Table 1. Study Assessments

Study Assessment	Baseline Assessment	Randomization Procedure	Discharge	7 Days (+/- 3 Days)	3 Months (+/- 15 Days)	6 Months (+/- 30 Days)	12 Months (+/- 45 Days)
Informed Consent	X	--	--	--	--	--	--
Eligibility Criteria	X	--	--	--	--	--	--
Medical history and Demographics	X	--	--	--	--	--	--
Baseline Physical	X	--					
Medication Assessment	X	X	X	X	X	X	X
12-lead ECG	X	--	X		X	X	X

Study Assessment	Baseline Assessment	Randomization Procedure	Discharge	7 Days (+/- 3 Days)	3 Months (+/- 15 Days)	6 Months (+/- 30 Days)	12 Months (+/- 45 Days)
Inclusion/exclusion	X	--	--	--	--	--	--
Holter Monitor						X	X
Adverse Events	--	X	X	X	X	X	X
Procedural Data	--	X	--	--	--	--	--
Protocol Deviations	X	X	X	X	X	X	X

3.3 Subject Lost to Follow-Up

The investigator will attempt to contact a subject at least three times prior to designating them as lost-to-follow-up subjects; two of these attempts should include attempting to contact subject via registered mail. The investigator will document the date and type of attempted communication and will complete the Study Exit/Completion Form when a subject is lost to follow-up.

3.4 Subject Withdrawals and Discontinuation

Subjects have the right to withdraw from the clinical investigation at any time and for any reason without prejudice to their future medical care by the investigation team or investigation site. The investigator will ask for the reason for their withdrawal and will record all information regarding the subject discontinuation on the Study Exit/Completion Case Report Form.

A subject may be withdrawn from the clinical investigation for the following reasons:

- Subjects may choose to withdraw from the clinical investigation under the terms of the Declaration of Helsinki and their consent documentation without having to give a reason;
- Any unanticipated adverse reaction which is, in the opinion of the Investigator, related to the treatment and will endanger the well-being of the subject if treatment is continued;
- Development of any intercurrent illness(es), infection or condition(s) that might interfere with the Clinical Investigational Plan;
- Non-compliance with the clinical investigation procedures deemed by the Investigator to be sufficient to cause discontinuation;
- Any problem deemed by the Investigator to be sufficient to cause discontinuation.

Investigator will treat all subjects discontinued from the investigation due to an unanticipated adverse reaction, directly related to the investigation, until the reaction resolves.

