Exclusion Criteria	
 1. LA diameter > 5.5 cm. 2. Left ventricular ejection fraction (LVEF) < 35%. 3. Presence of intramural thrombus, tumor or abnormality that precludes vascular access, catheter introduction or manipulation. 4. Coagulopathy, bleeding diathesis or suspected procoagulant state. 5. Known allergies or intolerance to anticoagulant and antiplatelet therapies to be used in conjunction with the study or contrast sensitivity that cannot be adequately pre-treated prior to the ablation procedure. 6. Positive pregnancy test results for female patients of childbearing potential or breast feeding. 7. Acute or chronic medical condition that in the judgment of the investigator would increase risk to the patient or deem the patient inappropriate to participate in the study. 8. Mitral valve stenosis and/or severe mitral regurgitation. 9. Valvular atrial fibrillation. 10. Prosthetic valves. 11. NYHA Class IV. 12. History of MI within 3 months prior to procedure. 13. Atrial septal defect (ASD) or left atrial appendage (LAA) closure device. 14. Atrial fibrillation from a reversible cause (e.g., surgery, hyperthyroidism, sarcoidosis or pericarditis). 15. Life expectancy < 12 months based on medical history or the medical judgement of the investigator. 16. Presence of any transvenous pacing, ICD or CRT leads. 																
Follow-up Visit Schedule	
  
 Subject Visit Description	Timeframe / Visit Window	
   
 Randomization Procedure	Day 0	
 
 Pre-Discharge	Prior to discharge from hospital following ablation procedure	
 
 7 days Follow-Up (Phone)	7 ± 3 days	
 
 3 Month Follow-Up	90 ± 15 days	
 
 6 Month Follow-Up	180 ± 30 days	
 
 12 Month Follow-up	365 ± 45 days	
 
 Unscheduled Visits	As needed/necessary	
  
	Subject Visit Description	Timeframe / Visit Window	Randomization Procedure	Day 0	Pre-Discharge	Prior to discharge from hospital following ablation procedure	7 days Follow-Up (Phone)	7 ± 3 days	3 Month Follow-Up	90 ± 15 days	6 Month Follow-Up	180 ± 30 days	12 Month Follow-up	365 ± 45 days	Unscheduled Visits	As needed/necessary
Subject Visit Description	Timeframe / Visit Window																
Randomization Procedure	Day 0																

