2.3 Secondary Endpoints

- Consistency of sources identified by the Ablacon EGF algorithm between the Randomization procedure and any applicable subsequent EGF-guided ablation procedures
- Freedom from documented episodes of AF recurrence following the blanking period (90 days post-ablation) through 12 months.
- Total number of EGF source ablations
- Total time of EGF source ablations
- Total fluoroscopy time and dose
- Overall procedure time

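### Section 3.4 lets the investigator end a subject's follow-up, not just study procedures, so the 12-month AF comparison may be biased by selective withdrawal, in an unknown direction

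*Combined protocol and SAP*

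**What the plan says.** Section 3.4 opens its list with "A subject may be withdrawn from the clinical investigation for the following reasons". Besides the subject's own choice, it gives four grounds that rest with the investigator: an unanticipated reaction "related to the treatment and will endanger the well-being of the subject if treatment is continued"; an intercurrent illness, infection or condition that might interfere with the plan; non-compliance; and "Any problem deemed by the Investigator to be sufficient to cause discontinuation". The investigator records the reason and related information on the exit form. The only continuation after exit is clinical: "Investigator will treat all subjects discontinued from the investigation due to an unanticipated adverse reaction", until it resolves.

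Section 2.6 sets the randomised alternatives as "immediate EGF-guided radiofrequency ablation with the Ablamap® Software System; or 2) EGF mapping followed by a cardioversion procedure, if required". The visit schedule in the Protocol Summary places this procedure on Day 0. Section 2.3 also foresees "any applicable subsequent EGF-guided ablation procedures".

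Table 1 (section 3.2) schedules ECGs at discharge and at 3, 6 and 12 months, Holter monitoring at 6 and 12 months, and adverse-event collection at every contact from the procedure onward. Section 2.7 plans Kaplan-Meier curves for AF recurrence and has no rule for withdrawn subjects or missing data.

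**The concern.** The reaction ground is worded for treatment that is still running. Here the randomised treatment is over at the end of the Day 0 procedure unless a later EGF-guided procedure takes place. For most subjects withdrawn after Day 0 there is little study treatment left to stop, and what exit removes is the remaining Table 1 assessments.

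The person deciding knows the allocation: section 2.6 has the investigator either ablate or choose whether to cardiovert, and no blinding is described. Kaplan-Meier estimation treats censoring as unrelated to prognosis. Exit because of a reaction, an illness, non-compliance or an unspecified problem may well be related to it.

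At stake are the comparison of AF recurrence from day 90 to 12 months, which is the one listed endpoint that measures longer-term rhythm outcome, and the later course of adverse events in subjects who leave.

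**Working it through.** **Reading the sections together**

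1. Unit of withdrawal (3.4): the whole investigation, not a procedure.
2. Treatment left after Day 0 (2.6, visit schedule, 2.3): none, unless a later EGF-guided procedure applies.
3. Data still to come after Day 0 (Table 1): adverse-event contacts at discharge, 7 days, 3, 6 and 12 months; ECGs at discharge, 3, 6 and 12 months; Holter at 6 and 12 months.
4. Provision to keep collecting outcomes after exit: none found in 3.3, 3.4 or 2.7. Section 3.4 promises care for a reaction but does not say that its course is recorded.

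**Inputs for an illustration**

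The plan gives no withdrawal rate, event rate or number randomised, so it has no figure to reproduce. The cap of 100 counts subjects enrolled at consent (2.5), and only those with sources above the threshold are randomised (2.6), so 50 per arm is the ceiling. The arm sizes, the 60% AF-free rate and the number withdrawn are assumptions.

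**Bias in the observed proportion**

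Let n be the EGF-arm size, f the number truly AF-free, w the number withdrawn before day 90, and a the number of those w who would have stayed AF-free. Subjects who leave before day 90 add nothing to a curve that starts at day 90, so

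observed freedom = (f − a)/(n − w).

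| n, f | w | all would have recurred (a = 0) | none would have recurred (a = w) |
|---|---|---|---|
| 40, 24 (60%) | 2 | 24/38 = 63.2% | 22/38 = 57.9% |
| 40, 24 (60%) | 4 | 24/36 = 66.7% | 20/36 = 55.6% |
| 25, 15 (60%) | 2 | 15/23 = 65.2% | 13/23 = 56.5% |
| 25, 15 (60%) | 4 | 15/21 = 71.4% | 11/21 = 52.4% |

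If those withdrawn recur at the arm's own rate (a = 0.6w), the result for n = 40 and w = 2 is (24 − 1.2)/38 = 60.0%, which is no bias.

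**Width of the uncertainty**

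When w of n outcomes are unknown, best- and worst-case bounds on the arm's proportion differ by w/n.

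- 50 per arm: 1/50 = 2 points, 3/50 = 6 points, 5/50 = 10 points.
- 30 per arm: 1/30 = 3.3 points, 3/30 = 10 points, 5/30 = 16.7 points.

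Now assume 70% AF-free among the EGF-arm subjects still observed, 50% in control, and 5 withdrawn from the EGF arm only.

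- 50 per arm: worst case 45 × 0.70/50 = 63%, best case (31.5 + 5)/50 = 73%. The 20-point difference could be 13 to 23 points.
- 30 per arm: worst case 25 × 0.70/30 = 58.3%, best case (17.5 + 5)/30 = 75%. The difference could be 8.3 to 25 points.

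**Power**

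For 50% against 70% at two-sided 0.05, losing 5 EGF-arm subjects moves power from 0.533 to 0.509 at 50 per arm, and from 0.349 to 0.319 at 30 per arm. The loss is small, so the issue is bias.

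**The case against.** There are several good points on the plan's side.

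- **The rule is permissive.** A reader might infer that section 3.4 forces subjects with complications out of the trial. It says only that they may be withdrawn. That stands, although discretion without criteria still allows selective loss.
- **The reaction ground is narrow.** It needs a reaction that is unanticipated, related to treatment, and dangerous if treatment continues. If no treatment remains, its last condition is seldom met after Day 0. That also stands on a literal reading. It shows that the wording does not fit the design, and the open-ended ground remains available for the same cases.
- **Loss of follow-up is not the only effect.** Section 2.3 foresees later EGF-guided procedures, which withdrawal could also prevent, and a reaction may occur during the Day 0 procedure itself. Loss of follow-up is the main effect.
- **Imbalance between arms is not shown.** A reader might infer that losses fall mostly in the ablation arm. That is plausible only for the reaction ground. Control subjects also undergo mapping and possible cardioversion, and the other grounds apply equally to both arms.
- **The direction of bias is not shown.** A reader might infer that AF freedom in the EGF arm is overstated. That requires those withdrawn to be mostly subjects who would have recurred. The opposite assumption reverses the sign, and control-arm withdrawals could offset or reverse it too.
- **The primary endpoints are largely protected.** Acute success is settled at the procedure, and a related serious event that prompts exit within 7 days has already occurred. Section 3.5 also commits to serious-adverse-event reporting guidance, whose content is not in the documents.

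None of this supplies a provision that keeps a withdrawn subject in follow-up.

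**Conclusion.** The concern holds in a limited form. Section 3.4 lets an investigator who knows the allocation end all follow-up on broad grounds, and nothing elsewhere in the plan keeps outcome collection going. The secondary AF-recurrence comparison may therefore be biased by informative censoring, and later adverse-event follow-up may be incomplete.

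Under the assumptions of 40 per arm, 60% AF-free and 2 to 4 EGF-arm withdrawals before day 90, the observed proportion moves up by 3.2 to 6.7 points or down by 2.1 to 4.4 points, depending on who leaves. Smaller arms widen this range. These figures show sensitivity and are not predictions, because the documents give no withdrawal rate. They do not support a claim about which arm loses more subjects or which arm gains. The change is worth making because a few exits matter in a trial with at most 100 enrolled and the remedy is cheap.

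**What to change.** In section 3.4:

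- Reconcile the clause about continued treatment with the Day 0 procedure in section 2.6 and the possible later procedures in section 2.3.
- State that the grounds decided by the investigator may end further study procedures but do not end follow-up.
- Keep these subjects in their randomised group, with the Table 1 assessments and adverse-event recording through 12 months, unless consent is withdrawn or the subject is lost to follow-up or dies. Record related reactions to resolution.

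In section 2.7:

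- Analyse these subjects as randomised, and add a best-case and worst-case sensitivity analysis for those who still exit.

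The open-ended ground need not be deleted once follow-up is separated from procedures. Clinical care and the subject's right to withdraw are unchanged. The cost is protocol wording and a few additional visits that are already on the schedule.
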